14.3 Safety	
14.3.1	Overall Summary of TEAEs (Analysis Population: Safety)
14.3.2	Incidence of TEAEs by System Organ Class and Preferred Term (Analysis Population: Safety)
14.3.3	Incidence of Treatment Emergent Related AEs by System Organ Class and Preferred Term
14.3.4	Incidence of Treatment Emergent Serious AEs by System Organ Class and Preferred Term
14.3.5	Incidence of TEAEs by Preferred Term in Descending Order of Frequency
14.3.6	Incidence of Treatment Emergent Related AEs by Preferred Term in Descending Order of Frequency
14.3.7	Summary of Lab Value and Change from Baseline
14.3.8	Shifts in Reference Range
14.3.9.1	Summary of Vital Signs and Change from Baseline: Pulse (bpm)
14.3.9.2	Summary of Vital Signs and Change from Baseline: Temperature (°F)
14.3.9.3	Summary of Vital Signs and Change from Baseline: Systolic Blood Pressure (mmHG)
14.3.9.4	Summary of Vital Signs and Change from Baseline: Diastolic Blood Pressure (mmHG)
14.3.10.1	Concomitant Medication Use by ATC Level 1 and WHO Preferred Term
14.3.10.2	Medication started on study by ATC Level 1 and WHO Preferred Term
14.3.10.3	Concomitant Medication Use by WHO Preferred Term in descending order of use
14.3.10.4	Medication started on study by WHO Preferred Term in Descending Order of Use
16- Listings	
16.1	Randomization List
16.2	Inclusion/Exclusion Criteria
16.3	Protocol Deviations
16.4	Early Terminations (Include date of ET and reason for ET)
16.5	Exclusions from PP
16.6	Demographics and Baseline Characteristics
16.7	Medical History
16.8	Concomitant Medications
16.9	WOMAC/PGA/OMERACT OARSIS Responder Status
16.10	Analgesic Used within 24 hours of visit
16.11	Adverse Events
16.12	Serious Adverse Events
16.13	Laboratory Values
16.14	Physical Exam (weight (lbs), Height, any abnormality (if listed)) and Vital Signs (BP, Temp, Pulse)
16.15	X-ray Data (and abnormalities, if listed)
16.16	OMERACT-OARSIS Responder Status (WOMAC A, C, and PGA)

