When the clinical trials of Ampion were designed, it was assumed that the vehicle for the product, saline, would have little to no effect in reducing pain, stiffness, or improving physical function. This control was determined not to be a true placebo, but rather turned out to be active treatment. To address this, Ampio proposed a 12-week Main Study (AP-003-C) with a 6:1 randomization to protect the blind and prevent any potential bias associated with an open label assessment. In follow up to the Main Study, Ampio is adding a 40-week add-on, open label study to address the safety of repeat injections for a year. The Open Label Study will also analyze efficacy using the Western Ontario and McMaster Universities Arthritis Index (WOMAC®) osteoarthritis Index 3.1, and the Patient's Global Assessment of disease severity (PGA). This study will analyze response according to these individual criteria as well as responder analysis of OMERACT-OARSI criteria.

The Osteoarthritis Research Society International (OARSI) and Standing Committee for Clinical Trials Response Criteria Initiative Outcome Measures in Rheumatology (OMERACT) committee, in concert with the international rheumatology community, worked to develop a uniform core set of outcome measures for osteoarthritis. While the committee initially developed two sets of responder criteria to present the results of changes after treatment in three symptomatic domains (pain, function, and patient's global assessment) as a single variable for clinical trials, the committee ultimately worked to create a simplified set of responder criteria, Scenario D, which captured the criteria for response.

In the original plan, for each domain, a response was defined by both a relative and an absolute change, with different cut-offs with regard to the drug, the route of administration and the OA localization. The formal OMERACT-OARSI scenarios defined a responder as:

- a. having achieved a high degree of improvement in pain or a moderate degree of improvement in 2 of the 3 response domains (pain, function, global assessment) (scenario A)

OR

- b. as having achieved a high degree of improvement in either pain or function, or a moderate degree of improvement in 2 of the 3 response domains (scenario B)

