5 STUDY PLAN AND PROCEDURES

Subjects will receive an IA injection of Ampion™ at Visit 9, Visit 11, Visit 13 and Visit 15 of AP-003-C-OLE. Telephone contact will be made with the subject 24 hours after each IA injection. The subject will be followed until Visit 17. Safety of repeat injections every 12 weeks for 36 weeks will be evaluated during every visit (in-clinic and telephone); in office-visits will evaluate vital signs, physical exam, adverse events, and blood tests (Visit 17 or Early Termination Visit 18 only). Clinical effects of treatment on OA pain will be evaluated during in-clinic visits at Visit 9, Visit 11, Visit 13, Visit 15 and Visit 17 using the WOMAC osteoarthritis Index 3.1 (pain subscore, stiffness subscore and function subscore) and an overall global severity assessment (Patient's Global Assessment [PGA]). The WOMAC will also be utilized to assess the contralateral knee pain at Visit 9 and Visit 17 (or Early Termination Visit).

The assessments and procedures performed at each subject visit or contact are described in Section 5.1 Description of Study Visits and in Table 6.1, Schedule of Assessments and Procedures.

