10.4 STUDY ENDPOINTS

10.4.1 Primary Endpoint

- Incidence and severity of treatment-emergent adverse events (TEAEs).

These incidents will be summarized by number and percent of subjects having an event, the number of events per subject, and frequency of events in study population.

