2. OBJECTIVES

2.1 Primary Objective

The primary trial objective is to carry on from the AP-003-C main study (one injection) and evaluate the safety of a 4-mL intra-articular (IA) injection of Ampion with repeat dosing every 12 weeks for 52 weeks and/or with five total injections of Ampion.

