4. HYPOTHESES AND METHODS

4.1 Primary Analysis Methodologies

Since this is an observational study on the repeat administration of Ampion 4 mL injection, no formal hypotheses will be tested in this study. There will be no comparisons made to threshold values or to “historical” control values. There is no comparator in this study.

All analyses will be descriptive in nature and will be performed at each efficacy assessment (Visit 9 (Enrollment), Visit 11 (Week 12), Visit 13 (Week 24), Visit 15 (Week 36) and Visit 17 (Week 40)). For dichotomous outcomes, the percentage of patients with that outcome will be estimated and exact 95% binomial confidence intervals will be calculated. These dichotomous outcomes are:

- The incidence of treatment emergent adverse events
- Responder status based on the OMERACT-OARSI responder criteria
- Evaluate OMERACT-OARSI ‘controlled’ responder defined as a 20% improvement in Pain and Function and 0.5 point absolute change in the 5-point Likert Scale
- Evaluate 20% improvement in PGA and 0.5 point absolute change in the 5-point Likert Scale

The outcomes with more continuous responses will be analyzed via descriptive statistics (n, mean, standard deviation, median, minimum, and maximum). Also, 95% confidence intervals from the mean response will be calculated. These outcomes are:

- Mean change and percent change in WOMAC A pain subscore
- Mean change and percent change in WOMAC B stiffness subscore
- Mean change and percent change in WOMAC C physical function subscore
- Mean change and percent change in PGA
- Mean Change and percent change in WOMAC A pain subscore questions 1 and 2 (pain with movement)
- Mean Change and percent change in WOMAC A pain subscore questions 3–5 (resting pain)
- Change in contralateral knee pain (WOMAC A)
- Change in contralateral knee stiffness (WOMAC B)
- Change in contralateral knee function (WOMAC C)

Differences in pain scores between successive visits will be estimated via descriptive statistics and confidence intervals.

The time to total knee replacement will be summarized using Kaplan-Meier methodologies. The use of rescue analgesia will be summarized as the dichotomous outcome on the number of patients using rescue medication and as continuous variables on the number of medications use.

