10.3 Figures	
10.3.1	OMERACT-OARSIS Responder Over 12 Weeks
10.3.2	WOMAC A Pain Scale Over 12 Weeks
10.3.3	WOMAC C Function Over 12 Weeks
10.3.4	PGA Over 12 Weeks
10.3.5	Rescue Med Use Over 12 Weeks

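### The SAP output list shows no by-injection safety table and no count of injections received, and its figures stop at 12 weeks in a 40-week repeat-dosing study

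*SAP*

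**What the plan says.** - **Objective.** SAP 2.1 asks for safety "with repeat dosing every 12 weeks for 52 weeks and/or with five total injections of Ampion". Protocol section 5 states: "Subjects will receive an IA injection of Ampion™ at Visit 9, Visit 11, Visit 13 and Visit 15 of AP-003-C-OLE". That is four injections in the extension, after one in the main study.
- **Prior exposure.** Protocol 1.2 describes a "12-week Main Study (AP-003-C) with a 6:1 randomization". SAP 2.4 names the arms as Ampion and saline. The entry criteria do not limit roll-over to the Ampion arm.
- **Primary summaries.** Under Protocol 10.4.1, TEAEs are "summarized by number and percent of subjects having an event, the number of events per subject, and frequency of events in study population". Protocol 10.4.2 adds body system, preferred term, seriousness, severity and relationship. Neither mentions injection number. SAP 5.2 ties a TEAE to the initial dose only.
- **Methods text.** SAP 4.1: "All analyses will be descriptive in nature and will be performed at each efficacy assessment", naming Visits 9, 11, 13, 15 and 17. TEAE incidence heads the list of dichotomous outcomes with exact 95% intervals.
- **Output list.** SAP section 7 has six TEAE tables (14.3.1 to 14.3.6), for example "Incidence of TEAEs by System Organ Class and Preferred Term (Analysis Population: Safety". No title in 14.1 to 14.3, or in Listings 16.1 to 16.16, refers to exposure or injections received.
- **Figures.** All five (10.3.1 to 10.3.5) are titled for 12 weeks, for example "OMERACT-OARSIS Responder Over 12 Weeks". SAP 5.2 puts the end of study at Day 280.

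**The concern.** The safety question particular to repeat dosing is whether reactions become more frequent or more severe with later injections. Answering it needs events tied to injections and a count of subjects at risk at each one. The methods text gestures at a by-visit TEAE incidence without defining it, and the output list does not visibly deliver it.

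Exposure matters in its own right. Visits can be missed and subjects can withdraw, and anyone given saline in the main study can reach at most four Ampion injections. No title shows that the report will state how many subjects received one, two, three, four or five.

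Timing also matters. SAP section 1 requires any analysis that is not in the SAP and is done after data review to be labelled post hoc. A by-injection safety table added at that stage would carry less weight than one specified now.

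**Working it through.** The plan gives no figure on this point, so the check compares titles with methods and then illustrates what pooling hides.

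**1. Count of titles (SAP section 7).** TEAE tables whose title names injection, interval or visit: 0 of 6. Tables or listings titled for exposure: 0. Figures titled for 12 weeks: 5 of 5. Read as extension weeks, that is 12/40 = 30% of follow-up and two of the five efficacy assessments (Visits 9 and 11).

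**2. Pooled summary under two risk patterns.** The per-injection risks are assumptions, taken as independent between injections. Proportion of subjects with an event = 1 − Π(1 − p_k).
- Rising 2, 4, 6, 8%: 1 − 0.98 × 0.96 × 0.94 × 0.92 = 18.6%. Events per 100 subjects: 2 + 4 + 6 + 8 = 20.
- Flat 5%: 1 − 0.95⁴ = 18.5%. Events per 100 subjects: 4 × 5 = 20.

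The pooled summaries differ by 0.1 percentage point, although risk rises fourfold in one case and not at all in the other.

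**3. What a by-injection table would show.** With 100 subjects dosed (the enrollment anticipated in SAP 2.4), Clopper-Pearson 95% intervals in the rising case are 0.2 to 7.0% for 2/100 at the first injection and 3.5 to 15.2% for 8/100 at the fourth. The pattern becomes visible, but the intervals overlap.

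**4. By-visit incidence as SAP 4.1 might be read.**
- Cumulative: 2.0, 5.9, 11.6, 18.6% (rising) against 5.0, 9.8, 14.3, 18.5% (flat). These do separate the patterns.
- Per visit interval: the nominal intervals are 84, 84, 84 and 28 days. Events at a constant daily rate giving 5% over 84 days give 1 − 0.95^(28/84) = 1.7% over 28 days, so unadjusted incidence would appear to fall after the last injection.

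The text does not say which reading is meant. It also includes Visit 9, where efficacy is scored before the first extension injection.

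**5. Follow-up after the last injection.** Visit 15 falls on Days 238 to 266 (252 ± 14) and Visit 17 on Days 266 to 294 (280 ± 14). The gap runs from 266 − 266 = 0 to 294 − 238 = 56 days, so a 28-day window is nominal, not assured.

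**6. Cumulative Ampion exposure.** Protocol 10.3.7 goes from 161 to 136 with 15% dropout: 161 × 0.85 = 136.85, which agrees. Assuming the 6:1 ratio applies to those who roll over:
- 161 subjects: 161 × 6/7 = 138 could reach five Ampion injections, and 23 at most four.
- 136 subjects: about 117 and 19.

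The one-sided 95% upper bound for an event never seen is 1 − 0.05^(1/n): 1.8% at n = 161 and 2.5% at n = 117. What can be said about five injections therefore depends on a count that no output title promises.

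**The case against.** A reader might infer that nothing planned separates the injections, and that the repeat-dosing question cannot be answered at all. The documents do not support that.

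- **Efficacy is separated.** SAP 4.1 plans results at each visit and differences in pain scores between successive visits. Protocol 10.4.2 plans a repeated-measures analysis and pairwise differences between administration time points with 95% intervals. WOMAC and PGA are scored before injection at Visits 11, 13 and 15, so these results do distinguish the injections.
- **TEAE incidence is nominally by visit.** If SAP 4.1 is followed and read cumulatively, it would separate the two patterns illustrated here. The near-identity of 18.6% and 18.5% holds only for the end-of-study total, and the risks were chosen to make that point.
- **Titles are not layouts.** SAP section 7 says the outputs will be provided in a separate document. A by-visit column inside a TEAE table, or dosing counts inside the accountability table, cannot be excluded. Listings of adverse events and of early terminations with dates are also planned, so some reconstruction by hand may be possible.
- **The figures concern efficacy and rescue use.** They do not bear on the safety endpoint, and their titles may be carried over from the 12-week main study.

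All of this stands and limits the point. It does not supply a rule assigning an event to an injection, a denominator, a common window or a count of injections received. At best, the methods text and the output list do not match on the primary endpoint.

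**Conclusion.** The point holds in a limited form. For the primary safety endpoint, the SAP's output list does not visibly carry through the by-visit TEAE incidence of SAP 4.1, and that incidence is itself undefined. No title counts injections received, and the figures as titled leave out Visits 13, 15 and 17. The efficacy analyses do not share the gap.

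Its size is best put as lost information. Under the assumed risks, a fourfold rise across injections moves the pooled incidence by 0.1 percentage point. This rests on illustrative, independent risks and on table titles, because layouts are not in these documents. The split into four or five Ampion injections assumes 6:1 among those who roll over, since actual arm counts are not given; the SAP's own main-study counts of 140 and 25 are 5.6:1 and sum to 165, not the stated 170.

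This is a worthwhile, inexpensive improvement to specify before the data are reviewed. It does not invalidate the study.

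**What to change.** In SAP section 7, with matching text in SAP 4.1:

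1. **Exposure table and listing.** Show extension injections received, total Ampion injections including the main-study arm, injection dates and days on study.
2. **TEAEs, related TEAEs and severity by injection number.** Assign each event to the most recent injection. Use subjects who received that injection as the denominator, with exact 95% intervals and a common 28-day post-injection window. Because the gap from Visit 15 to Visit 17 can be 0 to 56 days, also report actual follow-up after each injection or events per person-time. Show events after day 28 separately, and present results by main-study arm or cumulative Ampion count. State how events with partial start dates are assigned, since SAP section 9 can move a missing start date to the first dose.
3. **Figures 10.3.1 to 10.3.5.** Retitle and extend them over Visits 9 to 17.

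A table restricted to subjects who received all four extension injections should be left out, or kept only as a sensitivity analysis. It excludes those who stopped after an early reaction, so it biases the early risks low, and it should carry a note saying so.

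The cost is SAP wording and a few programs. Protocol 8.1 already requires the injection date and Protocol 9.3 the AE records; the main-study arm has to be merged in. The drawback is small counts per injection and wide intervals, so the tables would describe a pattern without establishing a trend.

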10.3 Figures	
10.3.1	OMERACT-OARSIS Responder Over 12 Weeks
10.3.2	WOMAC A Pain Scale Over 12 Weeks
10.3.3	WOMAC C Function Over 12 Weeks
10.3.4	PGA Over 12 Weeks
10.3.5	Rescue Med Use Over 12 Weeks

9. HANDLING OF MISSING OR INCOMPLETE DATES FOR ADVERSE EVENTS AND CONCOMITANT MEDICATIONS

9.1 Imputation Rules for Partial or Missing Stop Dates

If the month and year are present, impute the last day of the month. If only the year is present, impute December 31 of that year. If the stop date is entirely missing, assume the event or medication is ongoing. If a partial or complete stop date is present and the 'ongoing' or 'continuing' box is checked, then it will be assumed that the AE or concomitant medication stopped and the stop date will be imputed, if partial.

Start Date		Stop Date						Missing
		Complete: yyyymmdd		Partial: yyyymm		Partial: yyyy		
		<1 st Dose	≥1 st Dose	<1 st Dose yyyymm	≥1 st Dose yyyymm	<1 st Dose yyyy	≥1 st Dose yyyy	
Partial: yyyymm	=1 st Dose yyyymm	2	1	2	1	N/A	1	1
	≠ 1 st Dose yyyymm		2		2	2	2	
Partial: yyyy	=1 st Dose yyyy	3	1	3	1	N/A	1	1
	≠ 1 st Dose yyyy		3		3	3	3	
Missing		4	1	4	1	4	1	1

- 1 = Impute the date of first dose
- 2 = Impute the first of the month
- 3 = Impute January 1 of the year
- 4 = Impute January 1 of the stop year

Note: For subjects who were never treated (first dose date is missing), partial start dates will be set to the first day of the partial month.

Note: If the start date imputation leads to a start date that is after the stop date, then do not impute the start date.

10. SCHEDULE OF ASSESSMENTS AND PROCEDURES

	Enrollment	Post Treatment Phone Contact	Week 12	Post Treatment Phone Contact	Week 24	Post Treatment Phone Contact	Week 36	Post Treatment Phone Contact	Week 40 Final Visit	Early Termination
Visit # Day #	9 Day-170 to 0	10 24 hours post Visit 9	11 Day 84± 14 days	12 24 hours post Visit 11	13 Day 168 ± 14 days	14 24 hours post Visit 13	15 Day 252 ± 14 days	16 24 hours post Visit 15	17 Day 280 ± 14 days	18 Early Termination
Informed Consent	X									
Inclusion/exclusion criteria	X									
Medical history/prior medications ²	X						X			X
Concomitant medications	X	X	X	X	X	X	X	X	X	X
Physical examination	X		X		X		X		X	X
Vital Signs	X		X		X		X		X	X
WOMAC	X		X		X		X		X	X
Patient's global assessment (PGA)	X		X		X		X		X	X
X-ray ¹	X									X
Clinical laboratory tests	X								X	X
Urinalysis	X								X	X
Treatment with study drug	X		X		X		X			
Rescue medication dispensed	X		X		X		X			
Review Rescue medication	X	X	X	X	X	X	X	X	X	X
Adverse Events	X	X	X	X	X	X	X	X	X	X
